Recent data suggests that the intestinal microbiome can mediate the response to anti-obesity interventions. Roux-en-Y gastric bypass and vertical banded gastroplasty are associated with long-term alterations of the intestinal microbiome in humans and mice⁽²⁵⁻²⁷⁾. Colonization of germ-free mice with post-bariatric surgery feces resulted in less fat accumulation on standard mouse chow compared to colonization with stool from non-surgical obese patients⁽²⁶⁾. Animal models have highlighted the contribution of *Akkermansia*, a genus that is depleted in obese mice and humans but enriched after gastric bypass surgery^(25,27,28). Colonization of germ-free mice with the microbiome of mice following gastric bypass surgery resulted in weight loss and reduced adiposity compared to recipients of sham operated mice, associated with increased *Akkermansia*⁽²⁷⁾. Daily gavage of live but not heat-killed *Akkermansia muciniphila* reduced adiposity and hyperglycemia in mice with diet induced obesity⁽²⁸⁾. Interestingly, metformin treatment of mice on a high fat diet increases *Akkermansia muciniphila*, which has been proposed as a mechanism of its therapeutic effect⁽²⁹⁾. We recently demonstrated in a rodent model of Western diet-induced obesity that a high protein diet induces *Akkermansia muciniphila*, just as had been seen after bariatric surgery. Abundance of *Akkermansia muciniphila* was inversely correlated with body fat mass. Based on our preclinical rodent model data, we hypothesize that a high protein diet will shift the composition of the microbiome of obese subjects, including increased *Akkermansia*, and that this will result in an altered metagenome (abundances of bacterial genes).

AIM 3. Identify fecal microbial predictors of response to a high protein diet.

Rationale: We hypothesize that subjects will vary in the responsiveness of their microbiota to a HPD based on baseline or post-dietary intervention levels of microbes such as *Akkermansia muciniphila* that respond to the HPD. We will determine the time course of shifts in the microbiome and correlate these changes to weight loss and other metabolic parameters. Further understanding of the link between the microbiome and the beneficial effects of a high protein diet may spur development of therapies for obesity that directly target the microbiome to complement dietary modification.

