Data Analysis: Descriptive statistics (mean, standard deviation, median, inter-quartile range, and frequency distribution) of demographic information and baseline assessments will be generated to characterize the study participants. Patient characteristics and baseline measurements of the three diet groups will be compared using analysis of variance (ANOVA) for continuous variables, and Chi-square test for categorical variables to evaluate the appropriateness of the randomization. If the distribution of the variable is skewed, an appropriate variable transformation will be made before the comparison. Nonparametric methods, such as Kruskal-Wallis one-way analysis of variance, will also be used for comparison.

Primary Endpoint: the primary endpoint is change in body weight, which is calculated as the difference between Day 1 (baseline) and 16 weeks. The primary objective is to compare the weight loss between the high-protein diet and the standard diet. We will use ANOVA to compare the change in weight among the three groups (through contrast), and also use ANCOVA to compare the weight loss among these groups, adjusting for the baseline values and gender. If the primary endpoint is non-normally distributed, the Kruskal-Wallis one-way analysis of variance will be used.

Secondary Endpoints: The secondary endpoints are (1) efficacy variables: nutrition assessments (FFQ, 3DFR, and satiation questionnaire), anthropometric profiles (e.g., waist and hip circumferences), laboratory and biochemical variables (e.g., insulin, lipid levels, HbA1c), body composition (e.g., body fat), liver stiffness, microbiome changes, and level of hormones; (2) safety variables: incidence, severity and duration of adverse events, vital signs, concomitant medications and physical examination results.

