Shotgun reads will be inputted into HUMAnN2 for annotation of gene families and identification of the microbial source of these genes⁽⁷⁶⁾. Individual genes will be aggregated into functional pathways using the MetaCyc database⁽⁷⁷⁾. Gene and pathway abundance for the HPD and NPD groups at baseline will be compared to confirm that randomization prevented skewing of the functional profiles of the two groups. Pathway abundance will be fitted to a multivariate model using DESeq2 with diet group/time point, baseline BMI, age, sex, and smoking status as covariates to identify functional pathways impacted by a high protein diet after adjusting for covariates. Genes belonging to HPD-associated pathways, stratified by the genus of their microbial source, will then be individually evaluated using DESeq2. This approach will reduce the number of statistical tests which might be overwhelming given the greater than 5 million genes within the intestinal metagenome⁽⁷⁵⁾. HPD-associated genes will be visualized in pathway maps to highlight the specific metabolic shifts in the microbiome at the DNA level that occur on a HPD.

Expected results/potential pitfalls: We predict that a HPD will reduce the abundance of genes in phosphotransferase pathways involved in bacterial carbohydrate metabolism, which are elevated in obese humans⁽²⁴⁾. Our estimated final sample size of 80 subjects per group would be much larger than existing metagenomics studies of obese patients which have used 6-7 subjects per group at lower sequence depths (3 GB per sample in the most recent study)^(24,26). We anticipate that the magnitude of effect of a high protein diet will be less than that in those comparisons (obese vs. lean, gastric surgery vs. non-surgically managed) but that the 10 fold larger sample size will provide sufficient power to detect metagenomic shifts.

C. Aim 3. Identify fecal microbial predictors of response to a high protein diet.

Rationale and hypothesis: The second aim of this proposal focuses on the relationship of the microbiome to clinical endpoints including weight loss, body fat loss, lipids, and

hyperglycemia. We hypothesize that subjects will vary in the responsiveness of their microbiota to a HPD based on baseline or post-dietary intervention levels of microbes such as *Akkermansia muciniphila* that respond to the HPD. The impact of these microbial changes on diet-induced weight gain will be assessed in humanized gnotobiotic mice.

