Study design: This is a randomized study using the same subjects described in Aim 1. Nutritional assessment, physical examination, bioelectrical impedance, laboratories will be performed at baseline, and weeks 2, 4, 6, 8, 12 and 16. Stool samples will be collected on day 3, 7, 14, 17, 21, 28, 42, 56, 84 and 112.

Study timeline: Data collection will be completed at week 16. The stool samples collected during the study period will be used for 16S rRNA sequencing, shotgun metagenomics, and data analysis.

Bioinformatics protocol: Patient characteristics (physical measurements, lean body mass, laboratories, demographic traits) at baseline will be compared using a 2-sided t-test (for numerical variables) or chi-square test (for categorical variables) to evaluate the randomization. 3DFR and FFQ performed at each timepoint will be used to assess the predicted protein content of the patient's diet compared to baseline to evaluate the success of the dietary intervention. Clinical response endpoints significantly associated with HPD in Aim 1 will then be correlated with the abundance of microbes found to be enriched or depleted on a HPD in Aim 2.1. These endpoints will be fitted to multivariate models to adjust for baseline clinical covariates including BMI, age, sex, and smoking status. Spearman correlations will then be calculated for all combinations of residuals for the clinical endpoints and for microbial abundance (using DESeq2 fitted multivariate models from Aim 2.1 to adjust for covariates). Separate correlation analyses will be performed at baseline and each of the time points during treatment.

Microbes that are independently associated with clinical response to a HPD will then be used to create random forests classifiers to predict response. Subjects in the HPD group will be identified as responders if they had a decrease in any of the clinical endpoints that exceeded the predictions of the multivariate model for the NPD group. The sensitivity and specificity of the classifiers will be estimated using 10-fold cross-validation. Classifiers constructed from baseline microbial abundance and microbial data at each time point will be compared to determine the earliest time point when accurate predictions of response are possible.

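### Aim 3 does not name the endpoint's own baseline in the models that define responders, so for body fat, lipids and glucose the responder label tilts towards subjects with high starting values

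*Combined protocol and SAP*

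**What the plan says.** Section 4.C (Aim 3) concerns "clinical endpoints including weight loss, body fat loss, lipids, and" hyperglycemia. Its bioinformatics protocol first selects endpoints: "Clinical response endpoints significantly associated with HPD in Aim 1 will then be correlated with the abundance of microbes" that changed on the HPD in Aim 2.1. It then gives the adjustment: "These endpoints will be fitted to multivariate models to adjust for baseline clinical covariates including BMI, age, sex, and smoking status".

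These models are used in two ways:
- **Residuals.** "Spearman correlations will then be calculated for all combinations of residuals for the clinical endpoints and for microbial abundance", the microbial side being adjusted through the Aim 2.1 DESeq2 models. Those models also carry baseline BMI, age, sex and smoking status, but no baseline lipid, glucose or fat value.
- **Responder label.** An HPD subject is a responder "if they had a decrease in any of the clinical endpoints that exceeded the predictions of the multivariate model for the NPD group". This label is what the random forests are trained to predict, and "Classifiers constructed from baseline microbial abundance and microbial data at each time point will be compared" to find the earliest useful time point.

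In section 4.A, under Primary Endpoint, the ANCOVA for weight loss is specified as "adjusting for the baseline values and gender". Aim 3 does not refer to that model. It also does not say outright whether lipids and glucose enter as change or as level; the responder rule's wording points to change.

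**The concern.** The NPD model should predict what a given HPD subject would have done on the standard diet. On a change score, the starting value is a strong predictor of that: a subject with a high baseline reading tends to fall more on any diet. If the model omits the starting value, its prediction is too small a fall for high-baseline subjects and too large a fall for low-baseline subjects, and the responder label inherits that error.

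BMI with sex goes a long way towards representing baseline weight. It is a weaker stand-in for triglycerides, glucose or fat mass, and these may be the endpoints that reach Aim 3. In the preliminary isocaloric study (section 3.1 B) weight change did not differ between arms (p=0.80). Triglycerides and one of the two reported fat-mass comparisons (p=0.0395; the other gave p=0.17) are the results that favour high protein.

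At stake is the reading of Aim 3. The plan's own hypothesis ties candidate microbes to adiposity: in the rat model, *Akkermansia muciniphila* abundance "was inversely correlated with body fat mass" (section 1.C, rationale for Aim 2). If a baseline microbe is related to the observed starting value, it could be reported as predicting response to the HPD when it only marks who started high.

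**Working it through.** **Inputs from the plan.** 100 per arm (section 4.A, Study Design) and 20% dropout (section 4.B, 2.1) give 100 × (1 − 0.20) = 80 per group, which reproduces the plan's figure. The two-sided 0.05 level is stated for the Aim 1 secondary analyses and assumed here for the Aim 3 correlations.

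**Inputs not in the plan (assumed).** Baseline-to-week-16 correlation ρ of 0.5 to 0.8; microbe-to-baseline correlation of 0.2 to 0.4. The documents give neither.

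**1. Tilt for one endpoint, no diet effect.** Let z be the baseline in SD units. Given z, the change has mean −(1 − ρ)z and SD √(1 − ρ²). A prediction that ignores baseline is zero relative to the mean change, so

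P(responder | z) = Φ((1 − ρ)z / √(1 − ρ²)).

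- ρ = 0.5: 0.5/0.866 = 0.577, giving 72% at +1 SD and 28% at −1 SD.
- ρ = 0.8: 0.2/0.6 = 0.333, giving 63% at +1 SD and 37% at −1 SD.

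Averaged over z the share is 50%. The NPD arm regresses to the mean as much as the HPD arm does.

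**2. Any-endpoint rule, independent endpoints (assumed), one baseline at ±1 SD.** Share = 1 − (1 − P) × 0.5^(k−1).

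- k = 2: at +1 SD, 1 − 0.28 × 0.5 = 86% (ρ = 0.5) and 1 − 0.37 × 0.5 = 82% (ρ = 0.8). At −1 SD, 64% and 69% (68.5% before rounding P).
- k = 4: about 95-96% at +1 SD against 91-92% at −1 SD.

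**3. Baseline microbe with no diet-specific effect.** corr(change, baseline) = −√((1 − ρ)/2), which is −0.50 at ρ = 0.5 and −0.32 at ρ = 0.8. The induced correlation has size 0.2 × 0.32 = 0.06 to 0.4 × 0.50 = 0.20. By Fisher z at n = 80 (standard error 1/√77), a nominal 5% test rejects 9% to 43% of the time. The 0.2 to 0.4 must be what remains after BMI, age, sex and smoking.

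**4. Simulation with the listed covariates in the model.** 80 per arm, no diet effect, 1,500 replicates per setting, BMI correlated 0.3 with the endpoint's stable level, and a null microbe correlated 0.3 with one component of the baseline. Each row gives results at ρ = 0.5 / 0.7 / 0.9.

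| | Own baseline omitted | Own baseline added |
|---|---|---|
| Responders overall | 50% | 50% |
| Top v bottom baseline tertile | 71 v 29 / 66 v 34 / 59 v 41% | about 50 v 50% |
| False positives: microbe tracks observed baseline | 23 / 17 / 10% | 5 / 6 / 5% |
| False positives: microbe tracks transient fluctuation only | 43 / 43 / 45% | 17 / 27 / 37% |
| False positives: microbe tracks stable level only | 5 / 6 / 5% | 18 / 12 / 8% |

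A microbe unrelated to baseline gives 5-6% either way. For a weight-like endpoint (BMI correlation 0.9, ρ = 0.95), omitting own baseline gives 57% v 44% and 8% false positives.

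**The case against.** - **The covariate list is open.** It is introduced as inclusive, so a reader might infer that own baseline is excluded. The text supports only that it is not named. That still leaves the most influential covariate for these endpoints to be chosen after the data are seen.
- **Regression to the mean does not add responders.** A reader might infer that it does. The comparator regresses equally, and the share is 50% per endpoint with or without the covariate. What inflates the number is the zero-threshold any-endpoint rule: 1 − 0.5^k gives 75%, 87.5% and 93.8% for two, three and four independent endpoints. That is a separate matter, which this fix does not touch. The same rule dilutes the tilt, nearly to nothing at four endpoints. If few endpoints pass the Aim 1 screen, the tilt remains material.
- **Endpoints with no diet effect would normally not enter.** The percentages therefore do not describe admitted endpoints exactly. But a uniform diet effect d (in SD units) only changes the numerator in step 1 to (1 − ρ)z + d. Both shares rise and the dependence on z stays.
- **The link to microbes is thin.** The quoted correlation with body fat comes from rats after a diet phase, not from human baselines, and both sides of the Aim 3 correlation are already adjusted for BMI. A false predictor is therefore possible, not certain.
- **Baseline adjustment is not free for a non-randomised predictor.** This stands. Where a microbe tracks only the stable true level, adding a noisy measured baseline raises false positives from 5-6% to 8-18%. Where it tracks transient fluctuation, 17-37% remain.
- **Change or level is unstated.** Modelling the level without baseline does not rescue the plan. A microbe correlated 0.3 with baseline then correlates 0.3 × 0.5 = 0.15 to 0.3 × 0.8 = 0.24 with the week-16 level, and rejects 26% to 57% of the time at n = 80.

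**Conclusion.** The concern holds for body fat, lipids and glucose, and only weakly for weight, which baseline BMI largely represents. With own baseline left out, who is labelled a responder depends on starting level, although how many are labelled does not. For a single endpoint without a diet effect the split is about 63-72% against 28-37% at ±1 SD; it narrows as more endpoints feed the any-endpoint rule. Spurious baseline predictors are a conditional risk: they need a microbe related to the observed baseline value beyond BMI, age, sex and smoking. All sizes rest on assumed correlations, which the documents do not supply. The stronger reading, that the plan rules out baseline adjustment for every endpoint and so manufactures responders, is not supported. The primary weight comparison in Aim 1 is unaffected.

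**What to change.** In the Aim 3 bioinformatics protocol:

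1. State that each clinical endpoint is analysed as change from baseline.
2. Name the endpoint's own baseline value as a covariate in the NPD prediction model that defines responders. This is the clearest gain, because that model exists to predict the outcome on the standard diet.
3. Add it also to the endpoint models whose residuals enter the Spearman correlations, and report the correlations without it as a sensitivity analysis. A microbe that appears under only one of the two should be described as dependent on that choice.

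The baseline values are already collected under the week 0 assessments. The cost is one degree of freedom per model and one extra set of correlations. For the correlations there is also the risk, shown above, of a small spurious association when a microbe follows only the endpoint's stable true level; the sensitivity analysis is there to expose it.

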3. WORK ACCOMPLISHED

3.1. Toward Aim 1

A. A High Protein Meal Reduces Body Weight in Human Subjects with Adult Type II Diabetes: We have performed a preliminary study comparing the effects of high protein meal replacement (MR) vs. individualized diet plans (IDP) as recommended by the American Diabetes Association on weight loss and metabolic profile. A total of 104 obese patients with type II diabetes on oral hypoglycemic agents (51 male and 53 female), with obesity as defined as BMI $>25 \text{ kg/m}^2$, were randomized and 77 patients completed the 12-month study. The percentage of weight loss in the MR group ($4.57 \pm 0.81\%$) was significantly greater ($p < 0.05$) than in the IDP group ($2.25 \pm 0.72\%$). Fasting glucose was significantly reduced in the MR group ($126.4 \pm 4.9 \text{ mg/dL}$) compared with the IDP group ($152.5 \pm 6.6 \text{ mg/dL}$, $p < 0.0001$) at 6 months but not at 12 months.

Controlling for baseline levels, HgbA1c level, a long term marker for efficiency of glucose control, was improved by $0.49 \pm 0.22\%$ for those receiving MR relative to the IDP group ($p < 0.05$). Considerably more patients in the MR group reduced their use of sulfonylureas

($p<0.0001$) and metformin ($p<0.05$) as compared to the IDP group. In the 77 patients who completed the 12-month study, highly sensitive C-reactive protein (hs-CRP) was measured. While the two groups had the same baseline hs-CRP level (MR: 3.70 ± 0.75 mg/L vs. IDP: 3.66 ± 0.69 mg/L), significant decreases in hs-CRP were observed in the MR group (-26.3%, $p=0.019$) but not in the IDP group (-7.06%, $p=0.338$) at 6 months as well as 12 months (MR: -25.0%, $p=0.019$; IDP: -18.7%, $p=0.179$).

This preliminary study suggests that high protein meal replacement is a safe and viable strategy for weight reduction in obese type II diabetes mellitus patients resulting in beneficial changes in measures of glycemic control and reduction of medications. The marked reduction in inflammatory marker hs-CRP following weight loss may confer additional cardiovascular benefit. These studies are relevant to the current proposal in that they clearly demonstrate that in patients with type II diabetes there is a significant reduction in weight in subjects ingesting a high protein diet compared to a normal protein diet.

B. High Protein Meal Induced Weight Loss and Satiety in Obese

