- c. Subjects must be in good health as determined by medical history, physical examination, and screening clinical laboratory including chemistry panel and CBC.
- d. Must have stable smoking habits (or be non-smokers) for at least 6 months prior to screening and agree not to intend to change such habits during the course of the study.

- e. Subjects requiring the regular use of any prescription medication may be admitted to the study providing the dose is stable.
- f. Subjects must sign the VA Greater Los Angeles Healthcare System Institutional Review Board-approved written informed consent prior to the initiation of any study specific procedures or randomization.

Exclusion Criteria:

- g. Weight stability: Subjects reporting weight change of >3.0 kg in the month prior to screening.
- h. Any subject who has been on a very low calorie diet (<800 kcal/day) for a period of 4 months or more in the 12 months prior to screening, or who has lost >10 kg in the 6 months prior to screening.
- i. Any subject who has a history of diabetic gastroparesis or gastric emptying disorder.
- j. Use of any other investigational drug(s) within 8 weeks prior to screening.
- k. Abnormal laboratory parameters: Serum creatinine >1.6 mg/cL; Liver function tests, ALT, AST, Bilirubin results >2.0 times the upper limit of normal; Triglycerides >500 mg/dL; total cholesterol >350 mg/dL; TSH outside of normal range.
- l. Subjects who drink >1 alcoholic beverage per day.
- m. Has an implanted cardiac defibrillator.

Pregnant women or women likely to become pregnant during the course of the study may not participate in this study. Female subjects must not be able to conceive by reason of surgery, radiation, 1 year past the onset of menopause, or an approved method of contraception. No vulnerable subjects will be included in the study.

Procedures:

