i. Study Design: This randomized controlled study will assign approximately 200 subjects (100 each) to the following arms (Appendix 1): 1) High protein diet group based on 1 gram of protein per pound of lean body mass, and 2) Standard protein diet group as control based on 0.5 gram protein per pound of lean body mass with same calories. All participants will meet with a registered dietitian, physician or nurse practitioner to assist them with their diet efforts in all the arms. In the study, the percent energy from fat will be held constant at 30% and the differences in the diets relate only to the protein and carbohydrate contents (30% protein and 40% carbohydrate, and 15% protein and 55% carbohydrate respectively). At the initial visit patient will not be calorie restricted but will have standardization of their nutritional macronutrient intake based on their group randomization. At the 2 week visit patient will then begin a 1500 calorie restricted diet with the same macronutrient composition (ie. 30% protein and 40% carbohydrate, and 15% protein and 55% carbohydrate respectively for the high and standard protein groups).

ii. Number of Subjects: Approximately 200 healthy volunteers age 30 years and older with a BMI between 27 to 40 kg/m² will be able to take part in this study.

iii. Estimated Study Duration: Accrual period is 3-4 years; anticipated dropout rate is 20%; and total study duration is approximately 5 years (taking into account data analysis).

iv. Subject Eligibility: Subjects will be assigned an enrollment number after signing the informed consent form. The subjects will complete all the screening tests and procedures as listed. When a subject completes the screening tests and procedures, the subjects will be assigned a randomization number. Subjects will be randomized into one of the two diet groups as described in Appendix 1.

The practitioner at screening will obtain each subject's date of birth, sex, race, medical history, current medications, and smoking and alcohol history. The physician will perform complete physical examinations. Height will be measured using a standardized stadiometer, while the subject stands

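### Baseline metformin use is recorded but left out of the microbiome covariates, so Aim 3 could produce a false microbial predictor of response or mask a true one

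*Combined protocol and SAP*

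**What the plan says.** **Akkermansia and metformin.** The Aim 2 rationale in section 1 (repeated in section 2) states that "metformin treatment of mice on a high fat diet increases" *Akkermansia muciniphila*, and that this has been proposed as a mechanism of the drug's effect. The same organism is predicted to rise on the high-protein diet (section 4, Aim 2.1) and is the named example of a response-related microbe in Aim 3.

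**Who can enter.** Inclusion criterion e reads: "Subjects requiring the regular use of any prescription medication may be admitted to the study providing the dose is stable". The only exclusion that mentions diabetes is "Any subject who has a history of diabetic gastroparesis or gastric emptying disorder". Criterion c limits entry in a general way: "Subjects must be in good health as determined by medical history".

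**What is recorded.** Screening collects "medical history, current medications, and smoking and alcohol history". On study, the safety variables are "incidence, severity and duration of adverse events, vital signs, concomitant medications and physical examination results".

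**What is modelled.** The Aim 2.1 model (16S) has diet, time point, their interaction, baseline BMI, age, sex and smoking. The Aim 2.2 model (metagenome) has a combined diet and time term and the same four baseline variables. Both lists are closed. Under Aim 3, Bioinformatics protocol, the endpoint models "adjust for baseline clinical covariates including BMI, age, sex, and smoking status". The microbial side of each correlation uses residuals from the fitted Aim 2.1 models. Microbes found to be independently associated with response then go into random forest classifiers, with responders defined in the high-protein group only.

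**The concern.** By the protocol's own account, metformin may shift the microbe of most interest. It also marks diabetes, and the background (Diet Influence on Body Weight in Humans) says that weight loss may be harder for people with diabetes. Hyperglycemia is itself one of the Aim 3 clinical endpoints. A variable tied to both the microbe and the response is a confounder of the association between them.

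Randomisation does not help here. Aim 3 asks which subjects respond and whether their microbes differ. That is a comparison between subjects, with separate correlations at each time point and with responders drawn from one arm. Metformin use is not randomly allocated in that comparison.

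At stake is the interpretation of an Aim 3 finding. The protocol hopes it will point towards therapies that target the microbiome, so a marker of drug use or diabetes read as a microbial predictor would mislead. A true predictor could equally be missed.

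**Working it through.** **The plan's own figure.** Section 4, Study Design gives 100 subjects per arm. Aim 2.1 assumes 20% dropout: 100 × (1 − 0.20) = 80 per group, which matches the stated figure. The high-protein arm alone is therefore n = 80, and both arms pooled are n = 160. The plan does not say whether the Aim 3 correlations pool the arms.

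**Inputs that are assumptions.** The documents give no share of metformin users and no human effect on Akkermansia or on response. I take a share p of 5%, 10% or 20%, a shift d in log abundance of 0.5 or 1 SD, and a shift e in response of 0.5 or 1 SD. The microbe has no link of its own to response. The two-sided 0.05 level is from Secondary Statistical Analyses.

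**Formulas.** With v = p(1 − p), the induced correlation is

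r = v·d·e / √[(1 + v·d²)(1 + v·e²)].

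The chance that a test is significant is approximately Φ(z − 1.96) + Φ(−z − 1.96), with z = r√(n − 3).

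**Worked corner** (p = 20%, d = e = 1): v = 0.16, so r = 0.16/1.16 = 0.138.
- n = 80: z = 0.138 × √77 = 1.21, giving about 23%.
- n = 160: z = 0.138 × √157 = 1.73, giving about 41%.

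**Full range.** The simulation column is the Spearman step at n = 80, with 4,000 runs per row.

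| Users | d, e (SD) | r | Formula, n = 80 | Simulated, n = 80 | Formula, n = 160 |
|---|---|---|---|---|---|
| 5% | 0.5, 0.5 | 0.012 | 5% | 4.9% | 5% |
| 5% | 1, 0.5 | 0.023 | 5% | 5.5% | 6% |
| 5% | 1, 1 | 0.045 | 7% | 6.1% | 9% |
| 10% | 0.5, 0.5 | 0.022 | 5% | 4.6% | 6% |
| 10% | 1, 0.5 | 0.043 | 7% | 6.1% | 8% |
| 10% | 1, 1 | 0.083 | 11% | 9.0% | 18% |
| 20% | 0.5, 0.5 | 0.038 | 6% | 6.4% | 8% |
| 20% | 1, 0.5 | 0.073 | 10% | 8.7% | 15% |
| 20% | 1, 1 | 0.138 | 23% | 22.2% | 41% |

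**Two checks.**
- With the drug indicator in both residual models, the simulated rate returns to 4.6-5.4% in every row.
- If the drug affects only the microbe or only the response (20% users), there is no inflation: 4.9% and 5.0%. The problem needs both links.

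**The case against.** Several points on the other side stand.

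- **Size.** Most of the table is close to the nominal 5%. The large values need 20% users and 1 SD effects on both sides. On the planning SD of 10 in Sample Size Determination, where mean weight loss is in lbs, 1 SD means that users and non-users differ by about 10 lb. The good-health criterion may keep users few, and the cited metformin effect is in mice.
- **Direction.** A reader might infer that the omission favours Akkermansia as a predictor. The documents do not fix the direction. If metformin raises Akkermansia and people with diabetes lose less weight, the correlation with weight loss is pulled down and a true predictor is hidden.
- **Open wording.** The word *including* in the Aim 3 list leaves room to add a covariate to the endpoint models. It does not open the closed Aim 2.1 list that supplies the microbial residuals.
- **Prediction versus explanation.** A confounded marker can still predict, and Aim 3 is exploratory and limited to endpoints and microbes already linked to the diet. But the plan also looks for independent associations and draws mechanistic hopes from them, and for that purpose confounding matters.

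A reader might also infer that the omission biases the Aim 2 diet contrast. The documents do not support this. Randomisation balances baseline use in expectation. The preliminary diabetes study (section 3.1.A) does report: "Considerably more patients in the MR group reduced their use of sulfonylureas", and likewise for metformin (p<0.05). However, it enrolled only type II diabetics on oral agents, ran for 12 months and compared against individualised diet plans. This trial takes volunteers in good health for 16 weeks against an isocaloric control. A different change in drug use by arm is possible but not shown. A baseline covariate would not correct it, and dropping samples taken after a drug change would condition on an event after randomisation. Nor does the Study Schedule have a line for medication review, so dated changes are not shown to be captured.

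**Conclusion.** The concern holds for Aim 3. The protocol names a drug that may move its key microbe, admits users and records use at screening, but has no term for it on the microbial side of the Aim 3 correlations and names none on the endpoint side. The bias could run either way.

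Under the assumed 5-20% users and 0.5-1 SD effects on both microbe and response, the false-positive rate per test is about 5-23% at n = 80. The figure of about 41% applies only if both arms are pooled and every assumption sits at its extreme. With few users, or with 0.5 SD effects, the rate is close to 5%. The actual size cannot be known until the number of users is counted.

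The primary endpoint is not affected, and no bias in the Aim 2 diet contrast is claimed. The change is worth making because it is cheap and because an Akkermansia finding would otherwise be open to an explanation that the protocol itself supplies.

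**What to change.** - Add baseline metformin use (yes/no), and preferably diabetes status, to the covariates of the Aim 2.1 model and of the Aim 3 endpoint models, so that both sets of residuals are adjusted.
- Add the same terms to the Aim 2.2 model, because the Aim 3 pipeline is applied again to the metagenomic data.
- Repeat the Aim 3 correlations and the classifier without baseline metformin users, and report the number of users by arm beside both sets of results.

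The metformin term uses the medication list already taken at screening; diabetes status can come from the medical history taken at the same visit. The cost is one or two extra covariates, one rerun and a slight loss of precision. If users prove few, the results will barely change, and reporting that settles the question.
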